11.3. Clinical Laboratory Parameters

Clinical laboratory results (serum chemistry, hematology, coagulation and urinalysis) will be valued using conventional units of measurement and summarized by treatment group using descriptive statistics for baseline, maximum post baseline, minimum post baseline, and last observed values. Changes from baseline will also be summarized. All clinical laboratory results will be listed by patient.

The numbers of patients shifting from a 'low' or 'normal' test result at baseline to 'high' result at any post-baseline assessment will be summarized, as will the numbers of patients shifting from a 'normal' or 'high' result at baseline to 'low' result post baseline. Laboratory parameters with a CTCAE grading scale will be summarized in Range Change Abnormal (RCA) tables which categorize patients according to (1) their most extreme post-baseline severity grade, and (2) the severity grade at their last post-baseline evaluation. Parameters with a CTCAE grading scale for high values and a second scale for low values will be summarized in both directions. Some

urinalysis parameters with categorical outcomes will be summarized with the numbers of patients shifting from normal at baseline (e.g., negative or absent) to an abnormal result post baseline (e.g., positive or present).

11.4. Vital Signs

Vital signs (systolic and diastolic blood pressures, pulse, body temperature and respiration rate) will be summarized by treatment group using descriptive statistics for baseline, maximum post baseline, minimum post baseline, and last observed values. Changes from baseline will also be summarized. All vital signs will be listed by patient.

The numbers of patients with a result above the normal range at any post-baseline assessment will be summarized, as will the numbers of patients with a result below the normal range at any post-baseline visit. Normal ranges are:

- Systolic blood pressure: 90-120 mm Hg
- Diastolic blood pressure: 60-80 mm Hg
- Pulse rate: 60-100 beats/minute
- Body temperature: 97.8-99.1 °F
- Respiratory rate: 12-18 breaths/minute

11.5. Electrocardiogram Results

ECG results (QRS duration, PR interval and QTc Interval) will be summarized by treatment group using descriptive statistics for baseline, maximum post baseline, minimum post baseline, and last observed values. Changes from baseline will also be summarized. All ECG results will be listed by patient.

The numbers of patients with a result above the normal range at any post-baseline assessment will be summarized, as will the numbers of patients with a result below the normal range at any post-baseline visit. Normal ranges are:

- QRS duration: 80-100 msec
- PR interval: 120-200 msec
- QTc interval (Bazett or Fridericia formula): ≤ 430 msec for males; ≤ 450 msec for females

The numbers of QTc values in the ranges <480 msec; 480-500 msec; and >500 msec will be presented for the categories baseline, worst (maximum) post-baseline assessment, and last post-baseline assessment.

The overall clinical interpretation of each ECG acquisition will be classified on the ordinal scale normal, abnormal but not clinically significant, and abnormal with clinical significance. Overall clinical interpretation will then be summarized (1) for the categories baseline, worst (maximum) post-baseline assessment, and last post-baseline assessment and (2) in a shift table pairing the baseline and most extreme post-baseline classifications.

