Note: SBP=Systolic Blood Pressure. DBP=Diastolic Blood Pressure. Normal Range Temperature: 36.6°C to 37.3°C. Normal Range SBP: 90-120 mmHg. Normal Range DBP: 60-80 mmHg. Normal Range Respiratory Rate: 12-18 breaths per minute. Normal Range Pulse Rate: 60-100 beats per minute.

^[1] Each subject is represented once by their worst change. A range change can be either a change in a vital sign parameter value from baseline low or normal to post-baseline high or a change from baseline high or normal to post-baseline low. A subject can be included in both 'High' and 'Low' categories if applicable.

Table 14.3.4.16
12-Lead Electrocardiogram (ECG)
Safety Population

Parameter	Time Point	Placebo (N=xx)		Tarextumab (N=xx)	
		Result	Change from Baseline	Result	Change from Baseline
QRS Duration (msec)	Baseline ^[1]				
	n	xx		xx	
	Mean (SD)	xx.x (xx.xx)		xx.x (xx.xx)	
	Median	xx		xx	
	25 th , 75 th Percentile	xx, xx		xx, xx	
	Min, Max	xx, xx		xx, xx	
Maximum Post-Baseline	n	xx	xx	xx	xx
	Mean (SD)	xx.x (xx.xx)	xx.x (xx.xx)	xx.x (xx.xx)	xx.x (xx.xx)
	Median	xx	xx	xx	xx
	25 th , 75 th Percentile	xx, xx	xx, xx	xx, xx	xx, xx
	Min, Max	xx, xx	xx, xx	xx, xx	xx, xx
Minimum Post-Baseline	n	xx	xx	xx	xx
	Mean (SD)	xx.x (xx.xx)	xx.x (xx.xx)	xx.x (xx.xx)	xx.x (xx.xx)
	Median	xx	xx	xx	xx
	25 th , 75 th Percentile	xx, xx	xx, xx	xx, xx	xx, xx
	Min, Max	xx, xx	xx, xx	xx, xx	xx, xx
Last Observation Post-Baseline	n	xx	xx	xx	xx
	Mean (SD)	xx.x (xx.xx)	xx.x (xx.xx)	xx.x (xx.xx)	xx.x (xx.xx)
	Median	xx	xx	xx	xx
	25 th , 75 th Percentile	xx, xx	xx, xx	xx, xx	xx, xx
	Min, Max	xx, xx	xx, xx	xx, xx	xx, xx
PR Interval (msec)	Baseline ^[1]				
	[etcetera]	[:]	[:]	[:]	[:]

^[1] Baseline is defined as the last non-missing value prior to first dose of study drug.

Programmer notes: (a) continue for all electrocardiogram parameters (QRS duration, PR interval, QTc Interval)

Table 14.3.4.17
12-Lead Electrocardiogram (ECG) – Range Change Abnormal
Safety Population

ECG Parameter	Placebo (N=xx)	Tarextumab (N=xx)
n	xx	xx
Any Post-Baseline High ^[1]		
QRS Duration (msec)	xx (xx.x%)	xx (xx.x%)
PR Interval (msec)	xx (xx.x%)	xx (xx.x%)
QTc Interval (msec)	xx (xx.x%)	xx (xx.x%)
Low ^[1]		
QRS Duration (msec)	xx (xx.x%)	xx (xx.x%)
PR Interval (msec)	xx (xx.x%)	xx (xx.x%)
QTc Interval (msec)	xx (xx.x%)	xx (xx.x%)
Last Observation Post-Baseline High ^[1]		
QRS Duration (msec)	xx (xx.x%)	xx (xx.x%)
PR Interval (msec)	xx (xx.x%)	xx (xx.x%)
QTc Interval (msec)	xx (xx.x%)	xx (xx.x%)
Low ^[1]		

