QRS Duration (msec)	xx (xx.x%)	xx (xx.x%)
PR Interval (msec)	xx (xx.x%)	xx (xx.x%)
QTc Interval (msec)	xx (xx.x%)	xx (xx.x%)

Note: Reference ranges: QRS duration 80-100 msec; PR interval 120-200 msec; QTc interval ≤430 msec (males), ≤450 msec (females).

^[1] Each subject is represented once by their worst change. A range change can be either a change in an ECG parameter value from baseline low or normal to post-baseline high or a change from baseline high or normal to post-baseline low. A subject can be included in both 'High' and 'Low' categories if fits both categories.

Table 14.3.4.18
12-Lead Electrocardiogram (ECG) – QTc Interval
Safety Population

Time Point	Placebo (N=xx)	Tarextumab (N=xx)
Baseline ^[1]		
<480	xx (xx.x%)	xx (xx.x%)
480-500 msec	xx (xx.x%)	xx (xx.x%)
>500 msec	xx (xx.x%)	xx (xx.x%)
Worst (Maximum) Post-Baseline		
<480	xx (xx.x%)	xx (xx.x%)
480-500 msec	xx (xx.x%)	xx (xx.x%)
>500 msec	xx (xx.x%)	xx (xx.x%)
Last Observation Post-Baseline		
<480	xx (xx.x%)	xx (xx.x%)
480-500 msec	xx (xx.x%)	xx (xx.x%)
>500 msec	xx (xx.x%)	xx (xx.x%)

^[1]Baseline is defined as the last non-missing value prior to first dose of study drug.

Table 14.3.4.19
12-Lead Electrocardiogram (ECG) – Overall Interpretation
Safety Population

Time Point	Placebo (N=)	Tarextumab (N=)
Baseline ⁽¹⁾		
n	n	n
Normal	n (%)	n (%)
Abnormal NCS	n (%)	n (%)
Abnormal CS	n (%)	n (%)
Worst Post-Baseline		
n	n	n
Normal	n (%)	n (%)
Abnormal NCS	n (%)	n (%)
Abnormal CS	n (%)	n (%)
Last Observation Post-Baseline		
n	n	n
Normal	n (%)	n (%)
Abnormal NCS	n (%)	n (%)
Abnormal CS	n (%)	n (%)

Note: NCS = Not clinically significant, CS = Clinically significant. Percentages are based on the number of subjects with a non-missing response at each visit.

⁽¹⁾ Baseline is defined as the last non-missing value prior to first dose of study drug.

Table 14.3.4.20
12-Lead Electrocardiogram (ECG) – Overall Interpretation Shift from Baseline
Safety Population

Baseline ^[1]	Most Extreme Post-Baseline	Placebo (N=xx)	Tarextumab (N=xx)
Normal	Normal	xx (xx.x%)	xx (xx.x%)
	Abnormal - Not Clinically Significant	xx (xx.x%)	xx (xx.x%)
	Abnormal - Clinically Significant	xx (xx.x%)	xx (xx.x%)
Abnormal - Not Clinically Significant	Normal	xx (xx.x%)	xx (xx.x%)
	Abnormal - Not Clinically Significant	xx (xx.x%)	xx (xx.x%)
	Abnormal - Clinically Significant	xx (xx.x%)	xx (xx.x%)
Abnormal - Clinically Significant	Normal	xx (xx.x%)	xx (xx.x%)
	Abnormal - Not Clinically Significant	xx (xx.x%)	xx (xx.x%)

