Treatment Group	Subject ID	Visit	Sample collected?	Collection Date (Study Day)	Collection Time	Microscopic Exam Performed?	Bacteria	Cast	Crystals	RBC (cells/hpf)	WBC (cells/hpf)	Other test	Result (units)	Reference Range
Placebo Tarxatumab	003-xxx-xxx	SCREENING CYCLE 1 DAY 1	Yes No	ddmmmyyy (xx)	xx:xx	Yes No	Absent Present Not Done	Absent Present Not Done	Absent Present Not Done	xx	xx	x.xx	xx units	xx-xx

Listing 16.2.8.5
Vital Signs

Treatment Group	Subject ID	Visit	Vital Signs Measured?	Date (Study Day)	Time	Temperature (°C)	Pulse Rate (beats/min)	Respiratory Rate (beats/min)	Blood Pressure		Height (cm)	Weight (kg)
									(Systolic/Diastolic) (mmHg)	(mmHg)		
Placebo Tarextumab	003-xxx-xxx	SCREENING CYCLE X DAY X	Yes No	ddmmmyyyy	xx:xx	xx.x	xx	xx	xxx/xx		xxx.x	xx.x

Listing 16.2.8.6
ECOG Performance Status

Treatment Group	Subject ID	Visit	ECOG Assessment		Assessment Date (Study Day)	Score ^[1]
			Yes	No		
Placebo Tarextumab	003-xxx-xxx	SCREENING CYCLE X DAY X			ddmmmyyyy (xx)	x

^[1] 0 = Fully active, able to carry on all pre-disease performance without restriction; 1 = Restricted in physically strenuous activity, but ambulatory and able to carry out work of a light or sedentary nature (e.g., light housework, office work; 2 = Ambulatory and capable of all self-care, but unable to carry out any work activities. Up and about more than 50% of waking hour; 3 = Capable of only limited self-care, confined to bed or chair more than 50% of waking hour; 4 = Completely disabled. Cannot carry on any self-care. Totally confined to bed or chair; 5 = Dead.

**OncoMed Pharmaceuticals, Inc.
59R5-003 (Phase 2)**

**Listing 16.2.8.7
12-Lead ECG
Part 1 of 2**

Page 1 of x

Treatment Group	Subject ID	Visit	Was ECG Performed?	Date of Assessment (Study Day)	PR Interval (msec)	QRS Duration (msec)	QTc Interval (msec)	QTc Interval Formula
Placebo Tarextumab	003-xxx-xxx	SCREENING CYCLE X DAY X	Yes No	ddmmmyyy (xx)	xxx	xxx	xxx	Bazett Fridencia

Note: MH = Medical History

<second part of listing>

**OncoMed Pharmaceuticals, Inc.
59R5-003 (Phase 2)**

**Listing 16.2.8.7
12-Lead ECG
Part 2 of 2**

Page 1 of x

Treatment Group	Subject ID	Visit	Was ECG Performed?	Date of Assessment (Study Day)	Interpretation	If Abnormal, Describe Abnormality	If Abnormal, Clinically Significant?	Primary Associated AE	Primary Associated MH
Placebo Tarextumab	003-xxx-xxx	SCREENING CYCLE X DAY X	Yes No	ddmmmyyy (xx)	Normal Abnormal	Description	Yes No	AE term	MH term

Note: MH = Medical History

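### QTc values corrected by Bazett and by Fridericia are pooled in the same summaries and cut-offs, although the formula is recorded for each ECG

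*SAP*

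**What the plan says.** Section 11.5 of the SAP gives one normal range for QTc whichever correction was used: "QTc interval (Bazett or Fridericia formula): ≤ 430 msec for males; ≤ 450 msec for females". The continuous summary treats QTc as a single parameter: "ECG results (QRS duration, PR interval and QTc Interval) will be summarized by treatment group using descriptive statistics". It adds "Changes from baseline will also be summarized", without requiring that the baseline and later values share a formula. The categorical summary is also single: "The numbers of QTc values in the ranges <480 msec; 480-500 msec; and >500 msec will be presented for the categories baseline, worst (maximum) post-baseline".

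The shells in Appendix B follow this.

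- Table 14.3.4.16 instructs the programmer to "continue for all electrocardiogram parameters (QRS duration, PR interval, QTc Interval", so results and changes appear for one QTc row.
- Table 14.3.4.17 counts range changes against "QTc interval ≤430 msec (males), ≤450 msec (females", with no formula named.
- Table 14.3.4.18 has the rows baseline, "Worst (Maximum) Post-Baseline" and last observation, with no formula row or column.
- The QTc box plots listed in Appendix A (Figures 14.3.4.77 and 14.3.4.78) are single as well.

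Listing 16.2.8.7 in Appendix D has a column "QTc Interval Formula" by subject and visit, with Bazett and Fridericia as the entries. No table or figure uses that column. Nothing in the SAP names one formula for analysis, requires matched formulas, or plans a re-derivation.

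**The concern.** The two corrections are different scales that agree only at 60 beats/min. The plan permits both and then counts and subtracts their values as if they were one measurement.

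Two things follow if the data do contain both. First, a count above 480 or 500 msec no longer has one meaning: the same tracing can fall in different bands depending on the correction applied. Second, a patient whose formula changes between visits shows a change from baseline that contains the formula difference. A Fridericia baseline followed by a Bazett reading above 60 beats/min looks like prolongation. The reverse order can hide a real one. A reader of the tables could not tell which had happened.

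**Working it through.** The SAP gives no figure to reproduce here, so the check is of the texts above and of the size of the formula difference.

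**Inputs**

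- Definitions (standard, not printed in the SAP): QTcB = QT/RR^(1/2) for Bazett and QTcF = QT/RR^(1/3) for Fridericia, with RR = 60/pulse in seconds.
- Pulse 60 to 100 beats/min: the normal range in section 11.4, used for illustration only. It is a flagging range, not evidence of patients' actual rates.
- Uncorrected QT of 360 to 400 msec: an assumption, since the SAP gives no QT values.
- Cut-offs 430, 450, 480 and 500 msec: section 11.5.

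**Step 1: ratio.** QTcB/QTcF = RR^(1/3 − 1/2) = RR^(−1/6) = (pulse/60)^(1/6), whatever the QT.

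**Step 2: difference QTcB − QTcF for the same ECG (msec)**

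| Pulse | Ratio | QT 360 | QT 380 | QT 400 |
|---|---|---|---|---|
| 50 | 0.970 | −10.1 | −10.7 | −11.3 |
| 60 | 1.000 | 0.0 | 0.0 | 0.0 |
| 70 | 1.026 | 9.9 | 10.4 | 11.0 |
| 80 | 1.049 | 19.5 | 20.5 | 21.6 |
| 90 | 1.070 | 28.8 | 30.4 | 32.0 |
| 100 | 1.089 | 37.9 | 40.0 | 42.1 |

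**Step 3: crossing the plan's cut-offs.** A Fridericia value f becomes the Bazett value t at pulse 60 × (t/f)^6.

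- 430 becomes 450 at 78.8 beats/min.
- 450 becomes 480 at 88.4 beats/min.
- 460 becomes 480 at 77.5 beats/min.
- 480 becomes 500 at 76.7 beats/min.

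At 100 beats/min, 445 × 1.089 = 485 (across 480) and 465 × 1.089 = 506 (across 500). All these rates lie within the 60 to 100 range.

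**Step 4: switch within a patient.** Hold QT at 380 msec and pulse at 80. Fridericia gives 418.2 and Bazett 438.8. Fridericia at baseline and Bazett later therefore show about +20 msec with no change in the ECG, and the reverse order shows about −20 msec. At 100 beats/min the figure is about 40 msec in either direction.

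**Step 5: what could be rebuilt from the data.** Listing 16.2.8.7 shows PR, QRS, QTc and formula, but no uncorrected QT, RR or ECG rate. Listing 16.2.8.5 shows pulse by visit. A Bazett value can therefore be put on the Fridericia scale approximately, as QTcB × (60/pulse)^(1/6). For example, 490.6 at 100 beats/min returns 450.5.

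**The case against.** The strongest reply is that mixing is permitted but not shown. A listing shell stacks the possible entries of a field, so it establishes that the formula is captured by subject and visit, not that it varies. The listing has no site column, so variation between sites is conjecture. The protocol or CRF instructions, which are not at hand, may fix one formula. This stands as a limit on size. It does not alter the fact that section 11.5 names both formulas and directs one summary.

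A second reply is that the trial is randomised 1:1 and blinded, so the formula mix should balance between arms in expectation. That also stands. It does not repair a within-patient change or an absolute count. A bias between arms could arise if pulse differed by arm, because Bazett readings rise relative to Fridericia as the rate increases. That would persist in a Bazett-only table, so a split by formula alone does not remove it.

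Third, these are descriptive summaries with no test or decision rule, the progression-free survival analysis is untouched, and each value is listed with its formula so that a flagged case can be checked. All true, but a listing does not make the pooled counts interpretable.

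Some stronger readings are tempting and the SAP does not support them:

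- A reader might infer that QTc is the plan's only cardiac repolarisation check. Section 11.5 also summarises the overall clinical interpretation of each ECG, with a shift table (Tables 14.3.4.19 and 14.3.4.20), and adverse events are tabulated under section 11.2.
- A reader might infer that the worst-value rule selects the Bazett reading. That needs a patient with both formulas after baseline, a rate above 60, and underlying QT values that do not reverse the order. Below 60 beats/min Bazett is the lower value.
- A reader might infer that the error vanishes only if every ECG used one formula. For change from baseline, one consistent formula per patient is enough, and at 60 beats/min the formulas agree.

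**Conclusion.** The concern holds as a defect in how the QTc displays are specified. As written, section 11.5 and its shells pool two scales under one normal range, one set of bands and one change-from-baseline summary, and leave unused the field that would separate them.

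The difference for the same ECG is about 5% at 80 and 9% at 100 beats/min, or roughly 20 to 40 msec if QT is 360 to 400 msec. That is enough to move a reading across 480 or 500 msec. These sizes rest on the standard formula definitions, the assumed QT and the illustrative pulse range.

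The actual effect on the tables cannot be sized, because the SAP does not say how many ECGs use each formula or how many patients switch. Threshold counts are affected only where formulas are mixed, and change from baseline only where a patient's formula changes. The documents do not support saying that either has occurred, or that the arms are compared unfairly. The consequence is confined to descriptive safety summaries, but the remedy is cheap enough to adopt.

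**What to change.** - Present the QTc parts of Tables 14.3.4.16 to 14.3.4.18 and Figures 14.3.4.77 and 14.3.4.78 by the recorded formula, and say so in section 11.5.
- Compute change from baseline only from ECG pairs with the same formula.
- Keep every post-baseline ECG in the worst-value and 480/500 msec counts, shown by formula. Restricting these counts to the baseline formula could drop a reading above 500 msec and must be avoided.
- Add a supportive display on one scale, converting Bazett values with the same-visit pulse: QTcF = QTcB × RR^(1/6), RR = 60/pulse. This also addresses Bazett's dependence on heart rate, which the split alone leaves in place.
- If the data show that a single formula was used throughout, state that in the table footnotes; the split is then unnecessary.

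The cost is SAP and shell wording plus minor programming on data already collected. Numbers per display become smaller and some change-from-baseline pairs are lost. A patient with both formulas appears under each, so the columns cannot be added to give patients. Vital-sign pulse only approximates the rate at the ECG, so the converted values should remain supportive.

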11.6. ECOG Performance Status

ECOG performance status will be summarized (1) for the categories baseline, minimum post-baseline value, maximum post-baseline value, and last post-baseline value and (2) in a shift table pairing the baseline assessment and most extreme post-baseline values.

11.7. Immunogenicity

The incidence of anti-tarextumab antibody development in the tarextumab treatment group will be summarized with counts and proportions. In addition, the impact of detectable anti-tarextumab antibodies and neutralizing anti-tarextumab antibodies on the efficacy of tarextumab will be assessed by summarizing PFS and OS in the subgroups of patients with and without these anti-tarextumab antibodies. The impact of detectable anti-tarextumab antibodies and neutralizing anti-tarextumab antibodies on the safety of tarextumab will be assessed by comparing AE incidence rates in the subgroups of patients with and without these anti-tarextumab antibodies. However, these subgroup analyses may not be carried out if the number of subjects with or without anti-tarextumab antibodies does not provide reasonable estimates of PFS and ORR.

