	Abnormal - Clinically Significant	xx (xx.x%)	xx (xx.x%)

^[1] Baseline is defined as the last non-missing value prior to first dose of study drug.

Table 14.3.4.21
ECOG Performance Status
Safety Population

Performance Status Score ^[1]	Placebo (N=xx)	Tarextumab (N=xx)
Baseline ^[2]		
n	xx	xx
0	xx (xx.x%)	xx (xx.x%)
1	xx (xx.x%)	xx (xx.x%)
2	xx (xx.x%)	xx (xx.x%)
3	xx (xx.x%)	xx (xx.x%)
4	xx (xx.x%)	xx (xx.x%)
5	xx (xx.x%)	xx (xx.x%)
Maximum Post-Baseline		
n	xx	xx
0	xx (xx.x%)	xx (xx.x%)
1	xx (xx.x%)	xx (xx.x%)
2	xx (xx.x%)	xx (xx.x%)
3	xx (xx.x%)	xx (xx.x%)
4	xx (xx.x%)	xx (xx.x%)
5	xx (xx.x%)	xx (xx.x%)
Minimum Post-Baseline		
n	xx	xx
0	xx (xx.x%)	xx (xx.x%)
1	xx (xx.x%)	xx (xx.x%)
2	xx (xx.x%)	xx (xx.x%)
3	xx (xx.x%)	xx (xx.x%)
4	xx (xx.x%)	xx (xx.x%)
5	xx (xx.x%)	xx (xx.x%)
Last Observation Post-Baseline		
n	xx	xx
0	xx (xx.x%)	xx (xx.x%)
1	xx (xx.x%)	xx (xx.x%)
2	xx (xx.x%)	xx (xx.x%)
3	xx (xx.x%)	xx (xx.x%)
4	xx (xx.x%)	xx (xx.x%)
5	xx (xx.x%)	xx (xx.x%)

Note: Percentages are based on the number of patients with a non-missing response at each visit.

^[1] For complete definitions of each activity status code, reference Appendix D of the clinical protocol.

^[2] Baseline is defined as the last non-missing value prior to first dose of study drug.

Table 14.3.4.22
ECOG Performance Status – Shift from Baseline
Safety Population

Performance Status Score ^[1]	Placebo (N=) Baseline ^[2]		Tarextumab (N=) Baseline ^[2]	
	0	1	0	1
Maximum Post-Baseline				
n	n (%)	n (%)	n (%)	n (%)
0	n (%)	n (%)	n (%)	n (%)
1	n (%)	n (%)	n (%)	n (%)
2	n (%)	n (%)	n (%)	n (%)
3	n (%)	n (%)	n (%)	n (%)
4	n (%)	n (%)	n (%)	n (%)
5	n (%)	n (%)	n (%)	n (%)
Minimum Post-Baseline				
n	n (%)	n (%)	n (%)	n (%)
0	n (%)	n (%)	n (%)	n (%)
1	n (%)	n (%)	n (%)	n (%)
2	n (%)	n (%)	n (%)	n (%)
3	n (%)	n (%)	n (%)	n (%)
4	n (%)	n (%)	n (%)	n (%)
5	n (%)	n (%)	n (%)	n (%)

^[1] For complete definitions of each activity status code, reference Appendix D of the clinical protocol.

^[2] Baseline is defined as the last non-missing value prior to first dose of study drug.

Programming note: Continue for Last Observation Post-Baseline.

Programming note: Add additional baseline columns as needed.

Table 14.3.4.23
Anti-Tarextumab Antibodies
Immunogenicity Population

Time Point	Tarextumab (N=xx)
Any Positive Sample During Study	xx (xx.x%)
Cycle 1, Day 1	
Positive	xx (xx.x%)
Negative	xx (xx.x%)
Viable Sample Not Available	xx (xx.x%)
Cycle 3, Day 1	
Positive	xx (xx.x%)
Negative	xx (xx.x%)

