Viable Sample Not Available	xx (xx.x%)
Cycle 5, Day 1	
Positive	xx (xx.x%)
Negative	xx (xx.x%)
Viable Sample Not Available	xx (xx.x%)
Treatment Termination	
Positive	xx (xx.x%)
Negative	xx (xx.x%)
Viable Sample Not Available	xx (xx.x%)

Table 14.3.4.24
Impact of Anti-Tarextumab Antibodies on Progression-Free Survival
Immunogenicity Population

	Tarextumab (N=xx)	
	Anti-Tarextumab Antibody Negative (N=xx)	Anti-Tarextumab Antibody Positive (N=xx)
Total Follow-Up Time (person-years) ^[1]	xxx.x	xxx.x
Number of Subjects with Disease Progression or Death	xx (xx.x%)	xx (xx.x%)
Number of Subjects who did not Progress or Die (Censored)	xx (xx.x%)	xx (xx.x%)
Hazard ^[2]	0.xx	0.xx
Kaplan-Meier Estimates: Quartiles [95% C.I.] (days)		
25 th Percentile	xxx [xxx,xxx]	xxx [xxx,xxx]
50 th Percentile	xxx [xxx,xxx]	xxx [xxx,xxx]
75 th Percentile	xxx [xxx,xxx]	xxx [xxx,xxx]
Range (Subjects who Progressed or Died) (days)	xxx, xxx	xxx, xxx
Range (All Subjects) (days)	xxx, xxx	xxx, xxx
Hazard Ratio [95% C.I.] ^[3]		x.xx [x.xx,x.xx]
P-value ^[4]		0.xxx

Note: PFS= Date of Documentation of Death/Progression – Randomization Date + 1. Subjects who had not experienced death or progression by their last contact were censored at the time of their last radiographic response assessment. Subjects lacking a radiographic response assessment after randomization who do not progress or die have their event time censored on the date of randomization with duration of 1 day. For detailed event and censoring rules refer to protocol section 13.5.1 and SAP section 8.1. C.I. = Confidence Interval.

^[1]Sum of all individual follow-up times in days divided by 365.25.

^[2] Number of Subjects with Disease Progression or Death/ Total Follow-up Time (Person-years).

^[3] Hazard ratio and 95% C.I. from Cox proportional hazards model with main effects for anti-tarextumab antibody status (positive or negative).

^[4] P-value for treatment effect from unstratified log rank test.

Programmer notes: (a) percentages are based on the numbers of subjects who are antibody negative and antibody positive, not on the number of subjects receiving tarextumab

Table 14.3.4.25
Impact of Anti-Tarextumab Antibodies on Overall Survival
Immunogenicity Population

	Tarextumab (N=xx)	
	Anti-Tarextumab Antibody Negative (N=xx)	Anti-Tarextumab Antibody Positive (N=xx)
Total Follow-Up Time (person-years) ^[1]	xxx.x	xxx.x
Number of Subjects who Died	xx (xx.x%)	xx (xx.x%)

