Number of Subjects who did not Die (Censored)	xx (xx.x%)	xx (xx.x%)
Hazard ^[2]	0.xx	0.xx
Kaplan-Meier Estimates: [95% C.I.] (days)		
25 th Percentile	xxx [xxx,xxx]	xxx [xxx,xxx]
50 th Percentile (Median)	xxx [xxx,xxx]	xxx [xxx,xxx]
75 th Percentile	xxx [xxx,xxx]	xxx [xxx,xxx]
Kaplan-Meier Estimate (# at risk) [SE]		
180 Days	0.xx (xx) [x.xx]	0.xx (xx) [x.xx]
360 Days	0.xx (xx) [x.xx]	0.xx (xx) [x.xx]
540 Days	0.xx (xx) [x.xx]	0.xx (xx) [x.xx]
720 Days	0.xx (xx) [x.xx]	0.xx (xx) [x.xx]
Range (Subjects who Died) (days)	xxx, xxx	xxx, xxx
Range (All Subjects) (days)	xxx, xxx	xxx, xxx
Hazard Ratio [95% C.I.] ^[3]		x.xx [x.xx,x.xx]
P-value ^[4]		0.xxx

Note: Overall Survival = Date of Documentation of Death – Randomization Date + 1. Subjects who had not experienced death by their last contact date were censored at that time. Subjects lacking data after randomization who do not die have their event time censored on the date of randomization with duration of 1 day. For detailed event and censoring rules refer to protocol section 13.5.4 and SAP section 8.6. C.I. = Confidence Interval. SE = Standard Error.

^[1] Sum of all individual follow-up times in days divided by 365.25.

^[2] Number of Subjects who Died/ Total Follow-up Time (Person-years).

^[3] Hazard ratio and 95% C.I. from Cox proportional hazards model with main effects for anti-tarextumab antibody status (positive or negative).

^[4] P-value for treatment effect from unstratified log rank test.

Programmer notes: (a) percentages are based on the numbers of subjects who are antibody negative and antibody positive, not on the number of subjects receiving tarextumab

Table 14.3.4.26
Overall Summary of Impact of Anti-Tarextumab Antibodies on Treatment-Emergent Adverse Events (TEAEs)
Immunogenicity Population

	Tarextumab (N=xx)	
	Anti-Tarextumab Antibody Negative (N=xx)	Anti-Tarextumab Antibody Positive (N=xx)
Subjects Reporting at Least One TEAE	xx (xx.x%)	xx (xx.x%)
Subjects Reporting at Least One Serious TEAE	xx (xx.x%)	xx (xx.x%)
Subjects Reporting at Least One Serious TEAE Related to Tarextumab	xx (xx.x%)	xx (xx.x%)
Subjects Reporting at Least One Serious TEAE Related to Etoposide	xx (xx.x%)	xx (xx.x%)
Subjects Reporting at Least One Serious TEAE Related to Platinum Therapy	xx (xx.x%)	xx (xx.x%)
Subjects Reporting at Least One Grade 3 or Higher TEAE	xx (xx.x%)	xx (xx.x%)
Subjects Reporting at Least One Grade 4 or Higher TEAE	xx (xx.x%)	xx (xx.x%)

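### PFS and OS are compared from randomization by an undefined, post-randomization antibody status; read as any positive sample, the comparison is biased in favour of antibody-positive patients

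*SAP*

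**What the plan says.** Section 11.7 of the SAP states the question and the method: the effect of detectable and of neutralizing antibodies on efficacy "will be assessed by summarizing PFS and OS in the subgroups of patients with and without these anti-tarextumab antibodies". Adverse event rates are compared between the same subgroups. These subgroup analyses may be skipped if numbers are too small.

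The shells in Appendix B go further than a summary:

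- Tables 14.3.4.24 (PFS) and 14.3.4.25 (OS) split the tarextumab patients of the immunogenicity population into antibody-negative and antibody-positive columns, with no rule for who goes where.
- The clock starts at randomization in both: "PFS= Date of Documentation of Death/Progression – Randomization Date + 1" and "Overall Survival = Date of Documentation of Death – Randomization Date + 1".
- The comparison is a "Hazard ratio and 95% C.I. from Cox proportional hazards model with main effects for anti-tarextumab antibody status (positive or negative", with status entered once per patient.
- The footnote to the test reads "P-value for treatment effect from unstratified log rank test", although both columns are tarextumab patients and the contrast is antibody status.

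The only rule in the SAP that combines visits is in the incidence table, 14.3.4.23, whose first row is "Any Positive Sample During Study". The sampling times listed there are C1D1, C3D1, C5D1 and "Treatment Termination".

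Section 6.1 limits the immunogenicity population to patients with a baseline sample and at least one follow-up sample. The SAP contains no landmark, no time-dependent covariate and no other handling of the time before first positivity.

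**The concern.** Antibody status becomes known only after randomization, and a patient has to remain under follow-up to give the later samples. If one positive sample at any time makes a patient positive, the time before that sample is event-free by construction, yet the analysis counts it as survival time of the positive group. Patients who progress early have fewer samples and less time to convert, so those who enter the analysis do so mostly as negative.

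The direction is known: antibody-positive patients look better than they should. That is the direction that would hide a loss of efficacy caused by antibodies, which is the question section 11.7 asks. A hazard ratio with a confidence interval and p-value gives the result an inferential standing that it cannot carry.

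**Working it through.** **Inputs.** The SAP states no figure for the antibody comparison, so there is none to reproduce. The design inputs do check:

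- Table 3 treatment hazards are 0.65 times the control hazards: 0.65 × 0.1386 = 0.0901, 0.65 × 0.3466 = 0.2253 and 0.65 × 0.6931 = 0.4505 per month for 0-5, 5-7 and 7-8 months. Beyond 8 months the table gives 0.0451 or 0.1502.
- Power at 91 events, HR 0.67, one-sided 0.15: Φ(√(91/4) × |ln 0.67| − 1.036) = Φ(4.770 × 0.4005 − 1.036) = Φ(0.874) = 0.809. Table 1 gives 0.8090.

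Only the treatment hazards are used below, because both shells contain tarextumab patients only. C3D1 and C5D1 are taken as 42 and 84 days after the start, or 42/30.44 = 1.38 and 84/30.44 = 2.76 months. The termination sample is taken to fall at progression.

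**Assumption.** The SAP gives no seroconversion rate. Conversion is assumed unrelated to prognosis and without effect on PFS, so an unbiased analysis should give a hazard ratio of 1.

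**Mechanism.** Give each post-baseline sample the same chance p of being positive. A patient who progresses before C3D1 has one sample (termination), between C3D1 and C5D1 two, and after C5D1 three. The chance of being classed positive is 1 − (1 − p)^k for k samples:

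| p | k = 1 | k = 2 | k = 3 |
|---|---|---|---|
| 10% | 10% | 19% | 27.1% |
| 20% | 20% | 36% | 48.8% |

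Longer PFS therefore raises the chance of being called positive, although antibodies do nothing in this model.

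**Simulated PFS hazard ratio, positive versus negative, no true effect:**

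| Which samples count, and how conversion arises | Hazard ratio |
|---|---|
| C3D1 and C5D1 only, among patients event-free at C3D1; conversion 5-20% per month | 0.92-0.96 |
| C3D1, C5D1 and termination; fixed 10-20% chance per sample | 0.83-0.90 |
| C3D1, C5D1 and termination; conversion 5-20% per month | 0.24-0.46 |
| C3D1 landmark; conversion 5-20% per month | 0.98-1.02 |

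The third row is the most extreme because the chance of a positive termination sample rises with time on treatment. At 10% per month with the late hazard 0.0451, 48% of patients are ever positive, and median PFS is 7.8 months in positives against 4.2 in negatives. With the late hazard 0.1502 the share is 44% and the medians are 7.6 and 4.8 months. The second row is milder because every patient has the same chance at termination, however long the treatment lasted.

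With 67 patients, the nominal 5% log-rank test rejected in 5.6% to 12.3% of trials under the fixed-chance model, and in 80% to 100% under the accruing model, the latter without censoring.

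**Cost of the landmark.** The expected share event-free at C3D1 is exp(−0.0901 × 1.38) = 0.88, so about 12% of patients leave the PFS comparison.

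**The case against.** The strongest reply is that the shells never say ever positive. Section 11.7 and the column headings leave status undefined, and the any-positive row belongs to the incidence table, whose listed visits include C1D1. A reader might infer that the plan prescribes an ever/never split for PFS and OS. It does not; this is the likeliest reading, because no other across-visit rule exists and status enters the model as one fixed value. Patients already positive at C1D1 carry no immortal time. What is certain is that the columns are undefined and that nothing protects against the bias.

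Second, section 6.1 excludes patients without a follow-up sample, so early failures do not all fall into the negative group, as might be supposed. This stands in part. A termination sample qualifies a patient, so early progressors who give one still enter, mostly as negative. Even in the most favourable case in the table, the hazard ratio stays slightly below 1.

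Third, the size is set by assumptions. This stands. A reader might also be tempted by the control-arm hazards, which under the fixed-chance model give hazard ratios down to 0.79 and rejection in up to 16% of trials. Those figures do not apply to tables that contain only tarextumab patients.

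Fourth, it is tempting to extend the numbers to OS and adverse events. The structure of the OS shell is the same, so the argument carries over, but no OS figure was computed. For adverse events, more exposure brings more scheduled samples only up to C5D1; after that a single termination sample is listed. Longer exposure still allows more time to convert and more events, but this was not quantified.

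Finally, the analysis is supportive, may be dropped for small numbers, and controls no error rate. That limits the consequence, but the skip rule deals with sparse data, not with bias.

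**Conclusion.** The point holds in this form: the shells compare PFS and OS from randomization by an undefined antibody status treated as fixed, and under the only across-visit definition in the SAP the comparison favours antibody-positive patients. The direction does not depend on the seroconversion rate, provided that conversion is unrelated to prognosis and positivity can first appear after randomization.

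The size is not known. The simulated null PFS hazard ratios run from close to 1 (0.92-0.96) to grossly misleading (0.24-0.46), according to which samples count and how conversion accrues. The SAP settles neither, so none of these ranges should be quoted as the expected bias.

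The primary PFS analysis and the other randomized comparisons are not touched. The change is worth making because it is cheap and because, as written, the output could not answer the question that section 11.7 poses.

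**What to change.** 1. In section 11.7, define antibody-positive: which samples count, whether C1D1 positives are included or handled separately, and how neutralizing status is assigned.
2. For the efficacy comparison, use a C3D1 landmark: classify by status up to that visit, include only patients event-free then, and count PFS and OS from the landmark. The alternative is a Cox model with antibody status as a time-dependent covariate.
3. In 14.3.4.24 and 14.3.4.25, remove the fixed-status hazard ratio and the log-rank p-value on ever/never status.
4. In 14.3.4.26 and 14.3.4.27, report adverse events by status per patient-time or after the landmark.

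The cost is SAP wording and four shells, with no new data. The landmark drops about 12% of patients for PFS under the Table 3 treatment hazards, counts later converters as negative, and may leave few positives. The time-dependent model uses later conversions but does not fit the two-column Kaplan-Meier layout, and a first positive sample taken at termination for progression adds almost no positive follow-up time for PFS.
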